5.2.5 Left Ventricular Ejection Fraction

Effective after approval of CTPv6.0 MUGA is assessment is no longer applicable for ongoing patients.

Left Ventricular Ejection Fraction (LVEF) as measured by echocardiography or Multiple Gated Acquisition (MUGA) scan will be assessed as specified in the [Flow Chart](#). The same method of measurement must be used throughout the trial. LVEF assessment does not need to be repeated during screening if there is valid result available from an assessment which was performed as part of routine clinical practice within 28 days prior to start of trial treatment.

- Echocardiography will be performed to assess the LVEF according to the standard guidelines of the American Society of Echocardiography ([R06-1414](#)).
- MUGA scan is recommended for the assessment of diseases of the heart muscle. It is used for the monitoring of the ejection fraction of the cardiac ventricles, especially the LVEF.

Clinically relevant abnormal findings will be reported either as baseline condition (if identified at the screening visit) or otherwise as adverse events and will be followed and/or treated as medically appropriate.

5.2.6 Assessment of adverse events

5.2.6.1 Definitions of AEs

Adverse event

An adverse event (AE) is defined as any untoward medical occurrence in a patient or clinical investigation subject administered a medicinal product and which does not necessarily have to have a causal relationship with this treatment.

An AE can therefore be any unfavourable and unintended sign (including an abnormal laboratory finding), symptom, or disease temporally associated with the use of a medicinal product, whether or not considered related to the medicinal product.

Serious adverse event

A serious adverse event (SAE) is defined as any AE which fulfils at least one of the following criteria:

- Results in death,
- Is life-threatening, which refers to an event in which the patient was at risk of death at the time of the event; it does not refer to an event that hypothetically might have caused death if more severe.
- Requires inpatient hospitalisation or
- Requires prolongation of existing hospitalisation,

- Results in persistent or significant disability or incapacity, or
 - Is a congenital anomaly/birth defect,
- or**
- Is deemed serious for any other reason if it is an important medical event when based on appropriate medical judgement which may jeopardise the patient and may require medical or surgical intervention to prevent one of the other outcomes listed in the above definitions.

Examples of such events are intensive treatment in an emergency room or at home for allergic bronchospasm, blood dyscrasias or convulsions that do not result in hospitalisation or development of dependency or abuse.

AEs considered “Always Serious”

Every new occurrence of cancer of new histology must be classified as a serious event regardless of the duration between discontinuation of the trial medication and must be reported as described in [Section 5.2.6.2](#), subsections “AE Collection” and **AE reporting to sponsor and timelines**”.

In accordance with the European Medicines Agency initiative on Important Medical Events, Boehringer Ingelheim has set up a list of further AEs, which by their nature, can always be considered to be “serious” even though they may not have met the criteria of an SAE as defined above.

The latest list of “Always Serious AEs” can be found in the Electronic Data Capturing (eDC) system. These events should always be reported as SAEs as described above.

Adverse events of special interest (AESIs)

The term AESI relates to any specific AE that has been identified at the project level as being of particular concern for prospective safety monitoring and safety assessment within this trial, e.g. the potential for AEs based on knowledge from other compounds in the same class. AESIs need to be reported to the Sponsor’s Pharmacovigilance Department within the same timeframe that applies to SAEs, please see above.

The following are considered as AESIs:

Hepatic injury is defined by the following alterations of hepatic laboratory parameters:

- An elevation of AST and/or ALT ≥ 3 fold ULN combined with an elevation of total bilirubin ≥ 2 fold ULN measured in the same blood draw sample, and/or
- Aminotransferase (ALT, and/or AST) elevations ≥ 10 fold ULN

These lab findings constitute a hepatic injury alert and the patients showing these lab abnormalities need to be followed up according to the “DILI checklist” provided in the eDC system. In case of clinical symptoms of hepatic injury (icterus, unexplained encephalopathy, unexplained coagulopathy, right upper quadrant abdominal pain, etc.) without lab results (ALT, AST, total bilirubin) available, the investigator should make sure these parameters are analysed, if necessary in an unscheduled blood test. Should the results meet the criteria of hepatic injury alert, the procedures described in the DILI checklist should be followed.

Pneumonitis including interstitial lung disease, non-infectious pneumonitis and other analogous terms.

Intensity (severity) of AEs

The intensity (severity) of adverse events should be classified and recorded in the CRF according to the CTCAE version 5.0 ([R18-1357](#)).

Causal relationship of AEs

Medical judgement should be used to determine the relationship, considering all relevant factors, including pattern of reaction, temporal relationship, de-challenge or re-challenge, confounding factors such as concomitant medication, concomitant diseases and relevant history.

Arguments that may suggest that there is a reasonable possibility of a causal relationship could be:

- The event is consistent with the known pharmacology of the drug.
- The event is known to be caused by or attributed to the drugclass.
- A plausible time to onset of the event relative to the time of drug exposure.
- Evidence that the event is reproducible when the drug is re-introduced
- No medically sound alternative aetiologies that could explain the event (e.g. pre-existing or concomitant diseases, or co-medications).
- The event is typically drug-related and infrequent in the general population not exposed to drugs (e.g. Stevens-Johnson syndrome).
- An indication of dose-response (i.e. greater effect size if the dose is increased, smaller effect size if dose is diminished).

Arguments that may suggest that there is no reasonable possibility of a causal relationship could be:

- No plausible time to onset of the event relative to the time of drug exposure is evident (e.g. pre-treatment cases, diagnosis of cancer or chronic disease within days / weeks of drug administration; an allergic reaction weeks after discontinuation of the drug concerned)
- Continuation of the event despite the withdrawal of the medication, taking into account the pharmacological properties of the compound (e.g. after 5 half-lives). Of note, this criterion may not be applicable to events whose time cycle is prolonged despite removing the original trigger.
- Additional arguments amongst those stated before, like alternative explanation (e.g. situations where other drugs or underlying diseases appear to provide a more likely explanation for the observed event than the drug concerned).
- Disappearance of the event even though the trial drug treatment continues or remains unchanged.

5.2.6.2 Adverse event collection and reporting

5.2.6.2.1 AE Collection

The investigator shall maintain and keep detailed records of all AEs in the patient files.

The following must be collected and documented on the appropriate CRF(s) by the investigator:

- From signing the informed consent onwards until the end of treatment (including the Residual Effect Period, REP):

- All AEs (non-serious and serious) and all AESIs.
- After the end of treatment until the individual patient's end of trial:
- All drug-related SAEs and all drug-related AESIs.
- After the individual patient's end of the trial:

The investigator does not need to actively monitor the patient for AEs but should report drug-related SAEs and drug-related AESIs of which the investigator may become aware of by any means of communication, e.g. phone call. Those AEs should however, not be reported in the CRF.

The rules for Adverse Event Reporting exemptions still apply.

[figure not shown]

Figure 5.2.6.2: 1 AE collection periods

The REP is defined as 42 days after the last trial medication application. All AEs which occurred through the treatment phase and throughout the REP will be considered as on treatment. Events which occurred after the REP will be considered as post-treatment events.

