Collection of vital status information (21)										X	X	X	X (21)

* **Screening:** Documented HR/HER2 analyses results are required for the analysis of HR+ and HER2- status. If HR and HER2 status are unknown the patient is not eligible for screening.

** **Treatment:** From Cycle 1 to the end of Cycle 20 treatment cycles are 4 weeks in duration (28 days) with weekly visits for infusions and AE/concomitant medication documentation in addition to the CxV1 visits. From cycle 21 until the end of treatment cycles are 8 weeks in duration (56 days) with weekly visits for infusions and AE/concomitant medication documentation in addition to the CxV1 visits. Everolimus and exemestane should be dispensed every 4 weeks. Pregnancy testing (where applicable) to continue to be performed every 4 weeks (see footnote 25 below). Patients may continue on treatment for an unlimited number of cycles, until the criteria for stopping medication are met (see [Section 3.3.4](#)). Note: from cycle 3 onwards those patients that have discontinued xentuzumab/placebo, but remain on everolimus/exemestane will only be required to attend visits on day 1 (V1) of each cycle until the end of cycle 20 and on day 1 (V1) and day 29 (V5) of each cycle from the start of cycle 21.

*** **End of Treatment:** If the decision to permanently discontinue all study medication is taken during a scheduled visit, the EOT visit should be performed instead of the scheduled visit.

**** **End of Residual Effect Period/Follow up:** An EOR/FU1 visit must be conducted 42 days (+7 days) after the permanent discontinuation of treatment. If a patient has not progressed nor started further anti-cancer treatment prior to EOR/ FU1, the patient will continue to have regular follow-up visits for PD. FU_x-PD visits will take place (i) every 8 weeks (56 days) after EOT for patients who did not yet reach the end of cycle 20 and (ii) every 16 weeks (112 days) for patients who received treatment past cycle 20. These visits should be aligned with the imaging schedule. The FU-PD period will end at the time point of disease progression or start of further anti-cancer treatment.

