7.3.4 Safety analyses

Adverse events will be coded using the Medical Dictionary for Drug Regulatory Activities (MedDRA). Standard BI summary tables and listings will be produced. All adverse events with an onset between start of treatment and end of the REP, a period of 42 days after the last dose of trial medication, will be assigned to the on-treatment period for evaluation. As the treatment arms are made up of a combination of individual treatments a patient may have multiple last doses of treatment; therefore the last dose of study medication is defined as the latest of these.

All treated patients will be included in the safety analysis, according to the actual trial medication they received. In general, safety analyses will be descriptive in nature and will be based on BI standards. No hypothesis testing is planned.

Statistical analysis and reporting of adverse events will concentrate on treatment-emergent adverse events, i.e. all adverse events occurring between start of treatment and end of the residual effect period. Adverse events that start before first drug intake and deteriorate under treatment will also be considered as ‘treatment-emergent’.

Frequency, severity, and causal relationship of adverse events will be tabulated by system organ class and preferred term after coding according to the current version of the MedDRA at the database lock.

Laboratory data will be analysed both quantitatively as well as qualitatively. The latter will be done via comparison of laboratory data to their reference ranges. Values outside the reference range as well as values defined as clinically relevant will be summarised. Treatment groups will be compared descriptively with regard to distribution parameters as well as with regard to frequency and percentage of patients with abnormal values or clinically relevant abnormal values.

Vital signs, physical examinations, or other safety-relevant data observed at screening, baseline, during the course of the trial and at the end-of-trial evaluation will be assessed with regard to possible changes compared to findings before start of treatment.

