Subsequent anti-cancer therapy started before the outcomes flagged with a '*' above	Censored	Date of last radiological assessment before subsequent anti-cancer therapy (or date of randomisation if none exist)

* For these outcomes if initiation of subsequent anti-cancer therapy occurred prior to the outcome date then the rule for the final row of table will be used instead

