6. GENERAL ANALYSIS DEFINITIONS

6.1 TREATMENTS

For reporting purposes, all randomised patients will be classified into either 'Xe1000+Ev10+Ex25' or 'Plc+Ev10+Ex25' as randomised. For efficacy analyses, the intent-to-treat (ITT) approach will be used, i.e. patients will be analysed according to the treatment group they were randomised to. All planned analyses will be presented by this randomised treatment group. Handling of patients where treatment group assignment has not been followed will be handled on a case-by-case basis, to be agreed at report planning meetings prior to database lock. The following study periods are defined:

- Screening: day of informed consent to day prior to first administration of study treatment
- Treatment: day of first administration of study treatment to day of last administration of study treatment
- Residual effect period (REP): day after last administration of study treatment, for a duration of 42 days
- Follow-up: day after the end of the REP to trial completion

For safety analyses, treated patients will be analysed according to the initial treatment taken, and for safety summaries, data recorded whilst taking study treatment and up to 42 days after last administration of study treatment (i.e. including the REP) will be considered as on-treatment. As the treatment arms are made up of a combination of individual treatments, a patient may have multiple last doses of treatment; therefore, the last dose of study medication is defined as the latest of these.

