7.8.1 Adverse Events

AEs will be coded with the most recent version of the MedDRA. The severity of AEs will be scaled according to Common Terminology Criteria (CTC) AE version 5.

Unless otherwise specified, the analyses of AEs will be descriptive in nature. All analyses of AEs will be based on the number of patients with AEs and not on the number of AEs.

For analysis, multiple AE occurrence data on the eCRF will be collapsed into an AE if all of the following applies:

- All AE attributes are identical (Lowest Level Term [LLT], CTCAE grade, action taken with trial medication, therapy required, seriousness, reason for seriousness, relationship, outcome, AE of special interest)
- The occurrences are time overlapping or time-adjacent (time-adjacency of 2 occurrences is given if the second occurrence started on the same day or on the day after the end of the first occurrence).

For further details on the analysis and presentation of AE data refer to BI standards [\(5\)](#).

The analysis of AEs will be based on the concept of treatment emergent adverse events. That means that all AEs with an onset between first drug intake and last drug intake + REP (42 days) will be assigned to the randomised treatment. All AEs with an onset before first drug intake will be assigned to 'screening' and all AEs with an onset after the residual effect period will be assigned to 'post-treatment' (for listings only). For details on the treatment definition, see [Section 6.1](#).

An overall summary of AEs will be presented; along with the standard categories presented additional categories for action taken and drug relationship with each compound, worst CTCAE grade and infusion related reaction response. The frequency of patients with AEs will be summarised by treatment, highest CTCAE grade, primary SOC and PT. The SOC's will be sorted alphabetically; PT's will be sorted by decreasing frequency (within SOC). Only AEs with a given CTCAE grade will be displayed in tables showing AEs by worst CTCAE grade. AEs with a missing CTCAE grade will not be displayed in these tables; a footnote will explain that these AEs are not included and a separate listing of them will be produced if required. The following tables will be produced for AEs during the on-treatment period:

- Patients with AEs
- Patients with any related AE

- Patients with related xentuzumab/placebo AEs
- Patients with related everolimus AEs
- Patients with related exemestane AEs
- Patients with SAEs

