7.8.2 Laboratory data

The analyses of laboratory data will be descriptive in nature and will be based on BI standards (6). The same on-treatment periods as considered for the analysis of AEs will be applied for laboratory values. Patients having at least one post-baseline laboratory value will be displayed in the descriptive analyses.

The focus of the laboratory data analysis will be on the following primary laboratory parameters:

- Alanine aminotransferase (ALT), aspartate aminotransferase (AST), total bilirubin, glucose, creatinine, platelets, cholesterol, triglycerides, neutrophils, lymphocytes, haemoglobin and white blood cells.

Descriptive statistics including baseline, last value on-treatment and change from baseline to last value on-treatment will be produced. CTCAE grades for applicable laboratory parameters will be calculated according to CTCAE version 5. The following outputs will be presented for each of the above parameters:

- Transitions of CTCAE grade from baseline to worst on-treatment laboratory value
- Transitions of CTCAE grade from baseline to last on-treatment laboratory value

Patients with no CTCAE grade due to missing laboratory values will be displayed as 'Missing'. Note with version 5 of the CTCAE grading some of laboratory parameters detailed above (ALT, AST and total bilirubin) can no longer be assigned a grade at baseline. For these parameters, the CTCAE shift tables will be replaced by shift tables of pre-defined categories

based on Upper Limit of Normal (ULN) values. A similar approach will also be adopted for creatinine due the ambiguity of CTCAE grading for grades 2 and 3. The pre-defined categories will follow BI standards (7).

Possible clinically significant abnormal laboratory values are defined as those laboratory values that are of CTCAE Grade ≥ 2 and show an increase from baseline value by at least one CTCAE grade. For those parameters for which no CTCAE has been defined, BI standard definition will be used to determine possible clinical significance. Frequency of patients with possible clinically significant abnormal laboratory values will be provided whenever applicable. If no baseline value is available (or CTCAE grading at baseline cannot be assigned) but the patient has a post-baseline laboratory value of CTCAE Grade ≥ 2 an increase from baseline will be assumed, i.e. the laboratory value considered as possible clinically significant.

Hepatic enzyme elevations (potential Hy's law cases):

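### The on-treatment safety window runs to 42 days after the last dose even when a new anti-cancer therapy has started, so the all-causality tables can include next-line toxicity; supplementary truncated tables would show how much.

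*Protocol*

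**What the plan says.** Both documents give one rule.

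- Protocol 5.2.6.2.1: "The REP is defined as 42 days after the last trial medication application", and "All AEs which occurred through the treatment phase and throughout the REP will be considered as on treatment".
- Protocol 7.3.4 assigns to the on-treatment period: "All adverse events with an onset between start of treatment and end of the REP, a period of 42 days after the last dose". Where components stop on different days, the latest last dose counts.
- SAP 6.1: safety data recorded on treatment and "up to 42 days after last administration of study treatment (i.e. including the REP) will be considered as on-treatment".
- SAP 7.8.1 applies this window to AEs and assigns the events to the randomised treatment.
- SAP 7.8.2: "The same on-treatment periods as considered for the analysis of AEs will be applied for laboratory values".

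No visible text in these sections ends the window, or flags events, at the start of another anti-cancer therapy. Yet the footnote on the EOR/FU1 visit (day 42, +7 days) in the original protocol flow chart allows for such a start inside the window. Follow-up for progression continues "If a patient has not progressed nor started further anti-cancer treatment prior to EOR/ FU1", so some patients are expected to have started by then.

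The start date of subsequent therapy is collected (protocol 6.2.3.1 and 6.2.3.2), and SAP 6.6 has an imputation rule for it. SAP 5.1 and 5.2.2 use it for PFS, best overall response and pain progression.

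**The concern.** A patient who stops all trial drugs and starts chemotherapy two or three weeks later is still on treatment, by this definition, until day 42. A new AE, SAE or fatal AE from the chemotherapy enters the all-causality tables under her randomised arm. A low blood count up to day 42 can become her worst on-treatment laboratory value.

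The overlap is not hypothetical. Protocol 6.2.2.1 expects progression to be documented for most patients by FU1. Flow chart footnote 10 requires imaging before a new therapy in patients without objective progression. The rationale for global amendment 4 cites more early drop-outs with symptomatic progression than expected.

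The stake is how the all-causality safety summaries are read. With about 40 patients per arm, one patient moves a rate by 1/40 = 2.5 percentage points. The primary endpoint is not affected.

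**Working it through.** **1. Planning inputs.** Protocol 7.7 gives 80 patients (40 per arm), 15 months of accrual, 40 PFS events around month 30, medians of 9.9 and 19.8 months (hazard ratio 0.50) and about 20% losses. The point disputes no figure in the plan. As a check on the inputs, Table 7.7: 1 reproduces:

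- Φ[(ln 0.60 − ln 0.50)/(2/√40)] = 71.8%
- Φ[(ln 0.75 − ln 0.50)/(2/√40)] = 90.0%

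**2. Patients who leave by month 30.** Exponential hazards are ln 2/9.9 = 0.070 and ln 2/19.8 = 0.035 per month. The loss hazard is set at 0.02 per month (assumed, to give roughly the planned losses). Follow-up is uniform on 15 to 30 months. With total hazard r, the share leaving is 1 − (e^(−15r) − e^(−30r))/(15r).

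| | Control | Xentuzumab | Total |
|---|---|---|---|
| PFS events | 26.7 | 17.9 | 44.5 |
| Losses | 7.6 | 10.2 | 17.8 (22% of 80) |
| All exits | 34.3 | 28.1 | 62.4 |

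The event total is somewhat above the planned 40. Without a loss hazard the model gives 31.3 + 21.6 = 52.9 events, and 80% of that is 42.3. The inputs are close enough for an order of magnitude.

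**3. Patients with an added on-treatment AE.** The documents give neither the share starting new therapy within 42 days nor the chance of a new AE in the rest of the window. Both are assumed here, equal in the two arms: uptake 40% to 80%, AE probability 10% to 30%. Affected patients = patients leaving × uptake × AE probability, divided by 40 for a rate.

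| Uptake, AE probability | Who can contribute | Control | Xentuzumab | Gap (points) |
|---|---|---|---|---|
| 40%, 10% | PFS events only | 2.7% | 1.8% | 0.9 |
| 40%, 10% | All exits | 3.4% | 2.8% | 0.6 |
| 60%, 20% | PFS events only | 8.0% | 5.4% | 2.6 |
| 60%, 20% | All exits | 10.3% | 8.4% | 1.9 |
| 80%, 30% | PFS events only | 16.0% | 10.7% | 5.3 |
| 80%, 30% | All exits | 20.6% | 16.8% | 3.7 |

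At 60% and 20%, the gap is (26.7 − 17.9) × 0.12 = 1.1 patients on events only, and (34.3 − 28.1) × 0.12 = 0.7 on all exits. The second basis is the better one. Under protocol 7.7 the losses include patients with progression called by the investigator but not by independent review, and protocol 5.1 bases clinical decisions on the investigator's reading. These patients can also start new therapy.

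**4. Equal PFS.** With the same hazards in both arms, the exits are equal and the expected gap is zero. Both rates are raised by the same amount.

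**5. Deductions not made above.** SAP 7.8.1 counts patients at their highest grade, so an AE that a patient already had at the same or a higher grade adds nothing. Protocol 6.2.2.2 allows treatment beyond progression, so the clock starts at the end of all treatment, not at progression. The levels in step 3 are therefore likely to be too high.

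**6. Laboratory data.** The window closes on day 42. EOR/FU1 is due on day 42 (+7), so a scheduled sample on days 43 to 49 falls outside. Only samples up to day 42, scheduled or not, are affected.

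**The case against.** A fixed 42-day window is a defensible convention. At a terminal half-life of about 6 days (protocol 1.2.1) it covers 42/6 = 7 xentuzumab half-lives and keeps late drug effects. Protocol 5.2.6.1 defines an AE without regard to cause, so an all-causality table describes timing, not blame. The safety analysis is descriptive. SAP 7.8.1 has separate related-AE and related-SAE tables for each drug, and investigators are told to weigh other drugs. Protocol 5.2.6.2.4 exempts disease progression, and death due to it, from SAE reporting. Under the reduced schedule for ongoing patients, the combined end-of-treatment and end-of-residual-period visit comes at 7 to 14 days. All of this stands. It argues against replacing the main window, but it does not show how much next-line toxicity the all-causality tables contain.

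A reader might infer more than the documents support:

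- *That the rule loads toxicity onto the control arm and so hides xentuzumab toxicity.* This needs earlier treatment exit in the control arm. The visible SAP covers only the case where the expansion criterion is not met (SAP 3), and protocol 1.4 reports no added benefit of xentuzumab. Stopping for toxicity also opens a 42-day window and could reverse the direction.
- *That the SAP contradicts itself because PFS stops at new therapy and safety does not.* These are different derivations with different purposes, and overall survival is not censored at new therapy either (SAP 5.2.2).

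SAP 7.8.1 also refers to sponsor standards for further AE detail. These are not among the documents, so the point rests on the visible text.

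**Conclusion.** The point holds as a limited one. The on-treatment window takes no account of subsequent anti-cancer therapy, so the all-causality AE, SAE, fatal-AE and worst on-treatment laboratory summaries can include next-line toxicity. The related-AE tables are partly protected.

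The size is not derivable from the documents and is probably modest. With similar PFS in the arms, both rates are somewhat too high and no imbalance is expected. Under the planning hazard ratio of 0.50, the illustrative mid-case gives an imbalance of about 2 to 3 points, roughly one patient in 40. That figure rests on the assumed uptake and AE probability, both equal across arms, and on last dose at the time of exit. A systematic bias in favour of xentuzumab is not shown. This is a cheap improvement.

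**What to change.** Leave AE collection and the planned 42-day tables as they are. Add to SAP 7.8.1 and 7.8.2 supplementary tables for overall AEs, SAEs, grade 3 or higher AEs, fatal AEs and worst-grade laboratory values. End their window at the earlier of last dose plus 42 days and the day before the first subsequent systemic anti-cancer therapy. Flag events with onset after that day in the listings, so that a reader can see what was removed.

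The cost is one derived date, from data already collected and with an imputation rule already in SAP 6.6, plus a few tables. The downside is that the truncated tables may miss a late trial-drug effect first seen after the new therapy starts, which is why the planned tables should stay primary. Truncating by date alone also avoids making an all-causality table depend on causality judgement, as it would if later events were kept only when judged related.
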